8.8.2 Long-term Safety and Immune Persistence Study

Subjects will be followed up passively during a 12-month long-term safety observation after whole immunization to verify the incidence of serious adverse events during the study period. A visit (face-to-face/telephone visit) will be conducted once each at 3, 6, 9 and 12 months after full-course immunization to collect the data on the incidence of SAEs.

To observe the immune persistence in subjects who have completed the full-course immunization, about 5 ml of venous blood will be collected at 3 months (+30 d), 6 months (+30 d) and 12 months (+30 d) after the full-course immunization, and the serum will be separated for antibody detection and immune persistence evaluation.

8.9 Study Duration

For each subject it will last about 15 months from enrollment to discharge at the end of the final visit, and some subjects may terminate the study early at some point during the study.

This study will take about 16 months from the time the first subject is enrolled to the time the last subject is discharged at the end of the final visit.

8.10 Study Suspension/Early Termination

Criteria for suspension:

- The trial will be suspended in the event of 1 grade 4 or serious adverse event that may be related to vaccination during the study period;
- The trial will be suspended when more than 15% of subjects have experienced adverse events of grade 3 or above.

If the occurrence of adverse events meets the set criteria for suspension, firstly, the trial shall be suspended. Then, temporary DSMB meeting shall be held.

And the AE shall be reported to the national drug regulatory authority and the ethics committee, and the subject shall be notified. Based on the analysis of the correlation between adverse events, hazard degree and safety risks, investigation reports shall be formed and reported to relevant parties for them to decide whether to restart the clinical trial or not.

Criteria for early termination:

- The trial will be terminated early when there is 1 death that may be related to vaccination during the study period;
- When more than 30% of subjects have adverse events of Grade 3 and above, the investigators, sponsors and the data security monitoring committee will discuss together to decide whether to terminate the trial early;
- The sponsor requests full termination of the trial with justification;
- The administrative authorities request full termination of the trial with justification.
- The ethics committee requests full termination of the trial with justification.

9. Subject Population

9.1 The Selection of Subject Population

The target population is the local health population aged ≥ 18 , with the principle of voluntary participation. The volunteers shall participate the study after signing the informed consent form and passing the physical examination and the following inclusion and exclusion criteria screening. Investigators implementing the study, relevant study personnel and any employees of the contract research organizations (CROs) shall not be the subjects.

9.2 Inclusion Criteria

- Resident healthy adults aged 18 years and above;
- Volunteers give their consent and sign an informed consent form;
- Volunteers comply with the requirements of the clinical trial protocol.
- Axillary temperature $\leq 37.0^{\circ}\text{C}$.
- Female subjects of childbearing potential are not pregnant or breastfeeding at enrollment, and have no plans to have a baby within the first 3 months of enrollment; and they take effective contraceptive measures within 2 weeks prior to enrollment.

9.3 Exclusion Criteria

- Those subjects who have traveled abroad or have been to a village/community where an outbreak has occurred within 14 days prior to vaccination, have been exposed to COVID-19 infected or suspected cases, or are in quarantine, or come from their village/community where there are COVID-19 infected or suspected cases;
- Confirmed or suspected cases, or asymptomatic infections of COVID-19 (check the China Disease Prevention and Control Information System);
- Self-reported history of SARS virus infection;
- Positive RT-PCR test results on pharyngeal swabs;
- Those with a self-reported history of SARS virus infection;
- Those with previous severe allergic reactions to vaccination (e.g., acute allergic reactions, urticaria, skin eczema, dyspnea, angioneurotic edema, or abdominal pain) or allergic to known components of the inactivated novel coronavirus pneumonia (COVID-19) vaccine;
- Those with a history or family history of convulsions, epilepsy, encephalopathy or mental illness;
- Those with congenital malformations or developmental disorders, genetic defects, or severe malnutrition, etc.;
- Those known or suspected to have diseases including: severe respiratory disease, severe cardiovascular disease, severe liver or kidney disease, medically uncontrollable hypertension (systolic blood pressure ≥ 140 mmHg and diastolic blood pressure ≥ 90 mmHg; systolic blood pressure ≥ 150 mmHg and diastolic blood pressure ≥ 100 mmHg for subjects aged ≥ 60 years), complications of diabetes mellitus, malignancy, various acute diseases or acute episodes of chronic disease;
- Those diagnosed with congenital or acquired immunodeficiency, HIV infection, lymphoma, leukemia or other autoimmune diseases;
- Those with a history of coagulation abnormalities (such as deficiency of coagulation factors, coagulopathies);
- Those on anti-tuberculosis treatment;
- Those who have received other investigational drugs within 6 months prior to vaccination;
- Those who have received immune enhancement or inhibitor therapy within 3 months before vaccination (continuous oral or instillation for more than 14 d);
- Those who have received blood products within 3 months before vaccination;
- Those who have received a live attenuated vaccine within 14 days before vaccination;
- Those who have received other vaccines within 7 d before vaccination;

- Those with other conditions not eligible for participating in the study at the investigator's discretion.

9.4 Exclusion Criteria for Subsequent Vaccinations

After the enrollment, during the study period, if the COVID-19 epidemiological history, suspected COVID-19 clinical manifestations appear, epidemiological investigation and nucleic acid tests shall be carried out immediately, chest CT shall be taken if necessary, and the subjects shall undergo quarantine observation according to local epidemic prevention and control. If the subject is diagnosed with a COVID-19, he/she shall withdraw from the clinical trial, and accept the reasonable treatment from local center for disease control as required.

If one of the following (1) to (3) adverse events (AE) occurs, the vaccination shall be prohibited, other research procedures can be continued according to researchers' discretion; If one of the following (4) to (5) adverse events occurs, it is up to the investigator to determine whether the vaccination shall be continued; If one of the following (6) to (7) adverse events occurs, the vaccination shall be delayed within the time window specified in the protocol.

- (1) Any serious adverse events with cause association with vaccination;
- (2) Serious allergic response or hypersensitivity after the vaccination (including urticaria/rash within 30 minutes after vaccination);
- (3) Any diagnosed or suspected auto-immune diseases or immunodeficiency diseases (including human immunodeficiency virus (HIV) infection).
- (4) Emerging chronic diseases after vaccination or acute attack of chronic diseases;
- (5) Severe intolerable adverse reaction occurs.
- (6) Suffering from acute diseases at vaccination (acute diseases refer to moderate or severe diseases with or without fever);
- (7) Axillary temperature ≥ 37.0 °C at vaccination.

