10.4 Safety Observation

10.4.1 Definition of Adverse Events and Adverse Reactions

Adverse events: refer to all adverse medical events occurring to the subjects after receiving the investigational drugs, which are shown in symptoms, diseases or laboratory abnormalities. However, it is not always possible to deduce causal relationship between them and the experimental vaccines.

Adverse reactions: refer to all hazard or unexpected reactions for human that may be related to the experimental vaccines in clinical trials. There is at least a reasonable probability of a cause relationship between the experimental vaccines and the adverse event, that is, the correlation cannot be ruled out.

Serious adverse event: refer to all adverse medical events occurring to the subjects after receiving the investigational drugs, which are shown in death, life-threatening, permanent or serious disability, or the subjects need hospitalization or extended hospitalization and congenital abnormality or birth defect.

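### Section 9.4 leaves re-dosing after a related, non-serious Grade 4 reaction to the investigator's discretion, although 8.10 suspends the whole trial for such an event

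*Protocol*

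**What the plan says.** Protocol 8.10 sets the trial-level rule: "The trial will be suspended in the event of 1 grade 4 or serious adverse event that may be related to vaccination". Grade 4 and serious are alternatives, and either suffices. A suspension leads to a DSMB meeting and an investigation report, which goes to the relevant parties "for them to decide whether to restart the clinical trial or not".

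Protocol 9.4 sets the subject-level rules for later doses, in three tiers plus a withdrawal rule:

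- **Prohibited, items (1) to (3).** Item (1) is "Any serious adverse events with cause association with vaccination". Item (2) is serious allergy or hypersensitivity. Item (3) is autoimmune or immunodeficiency disease.
- **Discretionary, items (4) and (5).** Item (5) is "Severe intolerable adverse reaction occurs". For this tier, "it is up to the investigator to determine whether the vaccination shall be continued".
- **Delayed, items (6) and (7).** For acute illness or raised temperature at the time of vaccination, "the vaccination shall be delayed within the time window specified in the protocol".
- **Withdrawal.** "If the subject is diagnosed with a COVID-19, he/she shall withdraw from the clinical trial".

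Grade 4 is not named anywhere in 9.4. Protocol 10.4.1 defines an SAE by outcome, as events "which are shown in death, life-threatening, permanent or serious disability, or the subjects need hospitalization or extended hospitalization", or congenital abnormality or birth defect. It does not refer to severity grade.

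**The concern.** The protocol treats a related Grade 4 event as grave enough to stop dosing everyone, on the same footing as a related SAE. For the person who had the event, the two are then handled differently: the SAE ends that person's vaccination by rule, while the Grade 4 reaction that is not an SAE does not. No reason is given for the difference.

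At stake is the safety of an individual subject, and consistency. After a restart, two subjects with the same related, non-serious Grade 4 reaction could be treated differently, because a blinded investigator decides each case or because DSMB advice happens to cover one and not the other.

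**Working it through.** There is no figure in the plan to reproduce. The check compares the rules and then counts the injections after which the gap could matter.

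**1. Can an event be Grade 4 without being an SAE?** Yes, in a limited set of cases:

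- Table 9 grades axillary fever of 39.5°C or more for over 3 days as Grade 4. Neither admission nor threat to life is part of the criterion.
- Table 8 lists an abscess at the injection site as Grade 4, again without requiring admission.
- Table 8 grades pain as Grade 4 if basic self-care is lost or if the subject is hospitalized. These are alternatives, so admission is not required. This example also assumes that the loss of self-care is not judged a serious disability under 10.4.1.

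The test in 10.4.1 is whether hospitalization is needed, so each example counts only where it is not. The general Grade 4 wording for unlisted events in 10.4.4 refers to possible threat to life and will often coincide with an SAE. The point does not rest on it.

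**2. Which rules then apply to that subject?**

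- 9.4(1) does not apply, because the event is not serious.
- 9.4(2), 9.4(3) and the COVID-19 rule apply only if the event is of that kind.
- 9.4(5) is the closest fit and gives discretion.
- 9.4(6) and (7) at most postpone the dose.
- 8.10 decides the fate of the trial and attaches no dosing rule for the subject concerned.
- 10.4.8 requires treatment and follow-up for Grade 3 or above, but no stop to dosing. For pregnancy the same section does order vaccination stopped, so the protocol writes a hard stop where it wants one.
- 8.5 withdraws any subject who is emergency-unblinded, but unblinding happens only if the investigator thinks it necessary.
- 9.5(4) allows the investigator to exclude the subject.
- The visit schedules (Tables 2, 4 and 6) require vaccination screening before each later dose, which gives an occasion to stop but no instruction to.
- 10.9 lets the DSMB advise protective measures, which could include barring this subject.

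So several provisions may stop the next dose. For this event none must, unless emergency unblinding has taken place.

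**3. How many injections are exposed to the gap?** Inputs from Table 1: 250 + 250 = 500 subjects on three doses and 250 + 250 = 500 on two doses, each split 400 active and 100 placebo.

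- All planned injections: 500 × 3 + 500 × 2 = 2,500.
- Injections followed by another dose: 500 × 2 + 500 × 1 = 1,500.
- Of these, active: 400 × 2 + 400 × 1 = 1,200. Placebo: 100 × 2 + 100 × 1 = 300.

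The protocol gives no rate of related, non-serious Grade 4 events. Purely for scale, assumed rates of 0.01% and 0.1% per injection give 1,500 × 0.0001 = 0.15 and 1,500 × 0.001 = 1.5 subjects out of 1,000. These counts ignore the possibility that the trial does not restart or that the dosing window has passed.

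**The case against.** The strongest reply is that the case is already governed and that discretion is a legitimate choice. Item (5) assigns the decision to the investigator, 9.5(4) permits exclusion, and screening precedes every later dose. The trigger in 8.10 is a deliberately sensitive trial-level alarm, and a trial-level alarm need not equal a subject-level stopping rule. This largely stands. A reader might infer that the protocol has no rule for this subject, that the subject is re-dosed by default, or that 8.10 and 9.4 contradict each other. The documents support none of these readings: the case falls to discretion, and the two sections serve different purposes.

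The sequence is also narrow. The reaction must be Grade 4, related and non-serious, and must follow a non-final dose. The trial must be suspended, investigated and restarted. The next-dose visit has a window of 7 days (28 to 35 or 14 to 21 days after the previous dose), which a suspension could outlast. The examples are marginal too: Table 8 puts an aseptic abscess at Grade 3, so a Grade 4 abscess is something worse, and high fever prompts a COVID-19 work-up. All of this makes the event rarer. It does not supply a mandatory stop.

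Two cautions on reading remain. The DSMB charter is a separate document that is not at hand, so the gap can be asserted only for this protocol. The English text also uses serious and severe loosely (10.4.7 expands SAE with the word severe), so the line between items (1) and (5) should not be pressed hard. Still, 10.4.1 defines the serious adverse event by outcome, and item (1) uses that term.

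The discretion argument leaves one thing unexplained: for the other trigger in the same sentence of 8.10, the related SAE, 9.4 removes discretion.

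**Conclusion.** The point holds as a minor subject-safety improvement. Section 9.4 makes the stop mandatory for a related SAE but leaves a related, non-serious Grade 4 reaction to the investigator after a restart, subject to items (2) and (3), diagnosed COVID-19 and withdrawal after emergency unblinding.

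It is rare. It can arise only after 1,500 of 2,500 injections, and each case would already have suspended the trial and brought in the DSMB. The 0.15 to 1.5 subjects rest wholly on assumed rates and are not an estimate from the protocol. The conclusion assumes that item (1) uses serious as defined in 10.4.1 and that the DSMB charter or the restart decision adds no rule for the affected subject. Neither the primary analysis nor the sample size is affected.

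**What to change.** Change 9.4 item (1) to: *Any serious or Grade 4 adverse event with cause association with vaccination*. Keep item (5) at the investigator's discretion for reactions below Grade 4. The subject-level bar then matches the threshold that 8.10 already uses.

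The cost is a few words in a protocol amendment. A very few subjects would lose a later dose and with it membership of the per protocol set, which requires the full course (10.7.3.2). They would remain in the safety set and, with a pre-vaccination sample and valid antibody values, in the full analysis set. Their other study procedures, including blood sampling, could continue, as 9.4 already allows for items (1) to (3).

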9.5 Withdrawal or Discontinuation Criteria

If the subjects prematurely terminate the research, the researcher should record and dispose as follows:

- (1) Loss contact.
- (2) Death, the investigator shall record the reasons for death.
- (3) Voluntarily withdrawal, the investigator shall record the situation and the reasons for withdrawal:
 - Subjects advocated prematurely study termination (including vaccination termination, collection of biological specimen and safety observation, etc.), research data before withdrawal can be used for analysis. If the subject prohibits the investigator to continue to use all relevant research data, research data before withdrawal cannot be used for analysis.
 - The subjects advocate early termination of part of the study, for example, only stop the vaccination, or only stop the collection of biological specimens, other studies specified in the protocol shall be completed.
 - Subjects withdraw for reasons related to research, the specific withdrawal reason shall be recorded, researchers shall follow up the subjects who withdraw due to AE / SAE until the event was resolved.
 - Subjects withdraw for reasons unrelated to research (including out for a long time, migration), The investigator shall record the reasons for withdrawal.
- (4) Investigator exclusion

Subjects meet the exclusion criteria, emergency unblinding criteria, or investigator consider not suitable for participating in the research, the reason for exclusion shall be recorded.

10. Methods and Procedures

10.1 The Selection of Subjects

The local healthy volunteers aged ≥ 18 shall be enrolled, and provided with oral and written information of the study, and asked to sign the informed consent form.

After the signing of informed consent, the volunteers were screened according to the inclusion and exclusion criteria, qualified subjects can be registered into the group and assigned research number. Subjects from different age groups will be assigned to the corresponding study number according to the age from young to old.

10.2 Clinical Study Grouping and Number of Population Inoculated

See “8.2 Sample Size”.

10.3 Inoculation

10.3.1 Storage and Transportation of the Vaccines

The vaccines shall be stored and transported at $2 \sim 8^{\circ}\text{C}$, protected from freezing.

10.3.2 Inoculation Methods and Precautions

Observation objects that meet the inclusion criteria can be vaccinated, information of the experimental vaccine and the information of the subjects should be checked before vaccination, vaccines meet the requirements of the clinical trial protocol can be inoculated.

Inoculation site and route: inoculation site is lateral triangular muscle of upper arm, inoculation route is intramuscular injection.

The injection site shall be disinfected with 75% alcohol before injection, experimental vaccines shall be injected intramuscularly after the skin is slightly dry. The vaccine shall be well shaken before use. Experimental vaccines shall not be injected intradermally or subcutaneously. Subjects shall be carefully observed for at least half an hour after vaccination with the experimental vaccine, and appropriate emergency medical treatment measures should be prepared for serious allergic response after the vaccination.

10.3.3 Concomitant Medications and Concomitant Vaccination

Allowed medications: if the subjects experience AE during the clinical trial, necessary drug treatment is allowed, the name, administration route, reason and medication time shall be recorded.

Allowed vaccination: during the study period, subjects can receive routine immunization according to the product instruction, however, there needs an interval between routine inoculation and the previous dose of the experimental vaccine, it is 7 days for subunit vaccine and non-live vaccine, 14 days for live attenuated vaccine. Emergency vaccination for medical treatment is allowed, for example, rabies or tetanus vaccines can be timely inoculated according to the instructions. The name, usage, time and the vaccination site of concomitant vaccination shall be recorded.

10.4 Safety Observation

10.4.1 Definition of Adverse Events and Adverse Reactions

Adverse events: refer to all adverse medical events occurring to the subjects after receiving the investigational drugs, which are shown in symptoms, diseases or laboratory abnormalities. However, it is not always possible to deduce causal relationship between them and the experimental vaccines.

Adverse reactions: refer to all hazard or unexpected reactions for human that may be related to the experimental vaccines in clinical trials. There is at least a reasonable probability of a cause relationship between the experimental vaccines and the adverse event, that is, the correlation cannot be ruled out.

Serious adverse event: refer to all adverse medical events occurring to the subjects after receiving the investigational drugs, which are shown in death, life-threatening, permanent or serious disability, or the subjects need hospitalization or extended hospitalization and congenital abnormality or birth defect.

10.4.2 Observation time and method of adverse reaction

Subjects should be observed for immediate response at the inoculation site for 30 min after each must dose of vaccine, local / systemic adverse events within this period shall be recorded. Emergency equipment, drug and healthcare professional shall be available on site. The investigator shall closely follow the subjects within 7 days after each vaccination, ask the subjects to carry out safety observations on their own, the observation results shall be recorded on the daily diary card by the subjects. Subjects will be visited intensively by the investigator at day 7 after each vaccination to verify safety observations. Subjects shall carry out safety observations on their own from days 8-28 after each vaccination, and record the observation results on the daily diary card. Subjects will be visited intensively by the investigator at day 28 after each vaccination to verify safety observations.

During the study period, the serious adverse events shall be observed by initiative report of the subjects and regular visits of the investigators. The researchers shall carry out investigation and verification, and handle well after receiving serious adverse events reports A visit (face to face/telephone visit) will be conducted once each at 3, 6, 9 and 12 months after immunization to collect the data on the incidence of SAEs.

10.4.3 Safety observation indexes

Local reaction: pain, induration, swelling, rash, dizziness, pruritis, cellulitis.

Systemic reactions (including vital sign): fever, diarrhea, anorexia, vomiting, nausea, muscle pain, headache, cough, dyspnea, abnormal skin mucosa, acute allergic reaction, fatigue.

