8.7.2 Secondary endpoints

- Incidence of adverse events within 28 d after each dose of vaccine.

- Incidence of serious adverse events from the first dose to 12 months after full-course immunization.
- The antibody level of IgG antibody (ELISA method) against COVID-19 virus 28 days after the whole immunization
- Positive seroconversion rate and antibody level of neutralizing antibody and IgG antibody (ELISA method) against COVID-19 virus 28 days after the 2nd dose (as for 3-dose immunization group) or 14 days after the whole immunization (as for 2-dose immunization group)
- Positive seroconversion rates and the levels of novel coronavirus neutralizing antibodies and IgG antibodies (ELISA method) at 3, 6 and 12 months after full-course immunization.

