10.4.4 Safety assessment criteria

Adverse events after vaccination shall be judged according to grading criteria of *Guiding Principles of Grading Standards for Adverse Events in Clinical Trials of Preventive Vaccines* (National Drug Administration No. 102 of 2019)

Table 8. Rating Scale of Reaction Events at the Inoculation Site (Local)

Symptom/sign	Grade 1	Grade 2	Grade 3	Grade 4
Pain	No or minor impact on physical activities	Impact on physical activities	Impact on daily life	Loss of basic self-care ability, or hospitalization
Induration*, swelling**#				
Aged >14	2.5-<5 cm in diameter, or 6.25-<25 cm ² in area, and not or minor impact on daily life	5-<10 cm in diameter or 25-<100 cm ² in area, and impact on daily life	≥10 cm in diameter, ≥100 cm ² in area, ulceration, secondary infection, phlebitis, aseptic abscess, wound drainage, or severe impact on daily life	Abscess, exfoliative dermatitis, dermal or deep tissue necrosis
Rash*, areola**#				
Aged >14	2.5-<5 cm in diameter, or 6.25-<25 cm ² in area, and not or minor impact on daily life	5-<10 cm in diameter or 25-<100 cm ² in area, and impact on daily life	≥10 cm in diameter, ≥100 cm ² in area, ulceration, secondary infection, phlebitis, aseptic abscess, wound drainage, or severe impact on daily life	Abscess, exfoliative dermatitis, dermal or deep tissue necrosis
Pruritus	Pruritus at the inoculation site, relieved spontaneously or within 48 hours after treatment	Pruritus at the inoculation site, not relieved within 48 hours after treatment	Impact on daily life	NA
Cellulitis	NA	Non-injection therapy (e.g., oral antibacterial, antifungal and antiviral medication) is required	Intravenous injection therapy (e.g., intravenously antibacterial, antifungal and antiviral medication) is required	Sepsis, or tissue necrosis, etc.

Note: *In addition to measuring the diameter directly for grading evaluation, subsequent changes to the measurement results should also be recorded.

**The maximum measured diameter or area should be used.

#The indicators with higher grades should be selected based on the functional grade and actual measurement results for the evaluation and grading of induration, swelling, rash and areola.

Table 9. Vital Sign Rating Scale

Vital signs	Grade 1	Grade 2	Grade 3	Grade 4
Fever* [axillary temperature (°C)]				
Aged >14	37.3~<38.0	38.0~<38.5	38.5~<39.5	≥39.5, lasting for more than 3 days

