Dyspnea	Dyspnea during exercise	Dyspnea during normal activities	Dyspnea at rest	Dyspnea, and need for oxygen therapy, hospitalization or assisted breathing
Skin and subcutaneous tissue				
Abnormal skin and mucous membranes	Erythema/pruritus/color changes	Diffuse rash/maculopapule/dryness/desquamation	Blister/exudation/desquamation/ulcer	Exfoliative dermatitis with mucosal involvement, erythema multiforme, or suspected Stevens-Johnsons syndrome
Immune system				
Acute anaphylases**	Local urticaria (blisters) not requiring treatment	Local urticaria requiring treatment, or minor angioedema not requiring treatment	Extensive urticaria or angioedema requiring treatment, or minor bronchospasm	Anaphylactic shock, life-threatening bronchospasm or laryngeal edema
Others				

Fatigue	No impact on daily activities	Impact on normal daily activities	Severe impact on daily activities and inability to work	Emergency or hospitalization
---------	-------------------------------	-----------------------------------	---	------------------------------

Note: ** refers to type I hypersensitivity.

For adverse events not covered in the above scale, the intensity assessment should be performed according to the following criteria:

Grade 1 Mild: transient (<48h) or slight discomfort, which does not affect activities and not require treatment;

Grade 2 Moderate: mild or moderate activity limitation, which may require medical attention, no treatment, or only mild treatment;

Grade 3 Severe: significant restriction of activities, which requires medical attention, treatment, and possibly hospitalization;

Grade 4 Critical: it may be life-threatening, severely restricts activities, and requires monitoring and treatment.

Grade 5 Death

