10.7.4.4 Safety evaluation

AE is medically coded by MedDRA and counted according to the classification of SOC and PT. In addition, the collective adverse events will be counted according to the classification of systemic reaction and local reaction as specified by the protocol. The treatment emergency adverse events (TEAE) after inoculation are mainly counted and analyzed in this trial, that is, the AE occurred after first dose inoculation or the AE with aggravated severity after first dose inoculation. The AE incurred before first dose inoculation is listed. Unless otherwise stated, the following AE is TEAE.

The occurrence number, number of cases and incidence rate of all AE in each group, AE related to the vaccine study, AE unrelated to the vaccine study, AE of Grade 3 or above, AE of Grade 3 or above related to the vaccine study are calculated. The dose distribution, time distribution and severity of AE are statistically described. The list of AE related to the vaccine study, list of AE unrelated to the vaccine study and list of AE of Grade 3 and above are set out.

The occurrence number, number of cases and incidence rate of all AE in each group, AE related to the vaccine study and AE unrelated to the vaccine study are calculated, and the differences between groups are statistically compared by Fisher's exact test. The SAE list is set out.

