14.1 Vaccination

Subjects are not required to pay any fees for participating in this clinical trial, including physical examination, vaccination, and scheduled outpatient visits. During the study period, subjects will be compensated for transportation, lost labor, nutrition, etc. Subjects may be protected by the vaccine against COVID-19 for a period of time. Vaccination may cause some common adverse reactions. According to the literature, the incidence of adverse reactions to similar vaccines is very low and the reactions are slight. These adverse reactions may include pain, redness, swelling, fever, headache, nausea, vomiting, fatigue and other symptoms at the vaccination site. The subjects may get timely medical treatment in case of any serious adverse event related to or possibly related to the vaccination and when necessary, the “green channel for medical treatment” is started for emergency treatment.

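### Section 10.4.3 lists dizziness as a local reaction where Table 8 grades areola, and neither list in 10.4.3 names injection-site redness; used literally, this would misstate the local-reaction breakdown

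*Protocol*

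**What the plan says.** Protocol section 10.4.3 gives two lists of safety observation indexes. The local one reads "Local reaction: pain, induration, swelling, rash, dizziness, pruritis, cellulitis". The other reads "Systemic reactions (including vital sign): fever, diarrhea, anorexia, vomiting, nausea, muscle pain, headache, cough, dyspnea, abnormal skin mucosa, acute allergic reaction, fatigue". Redness, erythema and areola are in neither.

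Section 10.4.4 gives the grading scales. Table 8 covers the inoculation site and has rows for pain, induration with swelling, rash with areola, pruritus, and cellulitis. Its footnote says that the higher of the functional grade and the measured grade is used "for the evaluation and grading of induration, swelling, rash and areola". Table 9 grades fever, and Table 10 grades the systemic symptoms. For anything else there is a generic scale: "For adverse events not covered in the above scale, the intensity assessment should be performed according to the following criteria".

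Section 14.1 describes what may follow vaccination: "These adverse reactions may include pain, redness, swelling, fever, headache, nausea, vomiting, fatigue and other symptoms at the vaccination site".

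On analysis, section 10.7.4.4 says that "the collective adverse events will be counted according to the classification of systemic reaction and local reaction as specified by the protocol", in addition to MedDRA coding and tabulation by system organ class and preferred term. The related secondary endpoint in section 8.7.2 is "Incidence of adverse events within 28 d after each dose of vaccine".

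**The concern.** Dizziness is not a sign at the injection site. Redness is one, and the protocol both grades a sign that appears to be redness (areola) and names redness as expected. A list that contains the first and lacks the second conflicts with the grading table that immediately follows it.

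This is operative text. Section 10.4.3 is the only place that enumerates local and systemic reactions under those names, so it is the natural source for the diary-card prompts and for the classification that section 10.7.4.4 relies on. Subjects make their own observations on diary cards (section 10.4.2), and the terms they are prompted for influence what they report. At stake is the meaning of the local-reaction incidence, one of the summaries by which the two dose groups and the aluminium-adjuvanted placebo will be compared for safety.

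**Working it through.** The plan states no figure on this point, so the check is a term-by-term comparison.

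**Step 1. Local list (10.4.3) against Table 8 (10.4.4).**

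| Position | 10.4.3 local list | Table 8 | Match |
|---|---|---|---|
| 1 | pain | pain | yes |
| 2 | induration | induration | yes |
| 3 | swelling | swelling | yes |
| 4 | rash | rash | yes |
| 5 | dizziness | areola | no |
| 6 | pruritus | pruritus | yes |
| 7 | cellulitis | cellulitis | yes |

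Six of seven terms agree, in the same order. One term is only in the list (dizziness) and one only in the table (areola).

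**Step 2. All indexes against all scales.** Section 10.4.3 names 7 + 12 = 19 indexes. Tables 8, 9 and 10 grade 7 + 1 + 11 = 19 signs. Eighteen correspond one to one, allowing for synonyms such as vomiting and emesis, or muscle pain and myalgia. The only listed index without its own grading row is dizziness. The only graded sign without a listed index is areola.

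**Step 3. Does areola mean redness?** The protocol does not say so. The reading is an inference with two supports: Table 8 pairs areola with rash and grades both by diameter or area, and section 14.1 names redness next to pain and swelling.

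**Step 4. What follows if 10.4.3 is applied as written?**
- Dizziness, if reported, would be classed as local under 10.7.4.4, which adds to the local incidence.
- Redness would have no local term of its own. It might be reported unprompted, be placed under rash, or be left out of the local incidence, which could lower that incidence.
- The two effects run in opposite directions, and the protocol gives no rates for either event, so neither the net direction nor the size can be derived.
- The same list applies in every blinded arm. Nothing here favours one arm in collection; what changes is what the local rate measures.

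**Step 5. What does not follow?**
- Both events would still be coded by MedDRA and tabulated by preferred term if reported, so the incidence of adverse events by term does not depend on the list.
- Dizziness is not in the systemic list, and correcting the local list does not put it there, so the incidence of the listed systemic reactions is unchanged.
- The primary endpoints are immunogenicity endpoints, and the sample size in 10.7.2 rests on seroconversion rates. Neither uses these lists.

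**The case against.** The strongest reply is that this is a slip of wording, not a decision. The English text reads as a rough translation (Table 2 still carries a Chinese character in a visit heading), and the near-perfect match with Table 8 suggests that areola was meant. The documents that fix what subjects are asked, the diary card and the eCRF, are not shown and may carry the right term. Section 10.4.1 defines adverse events broadly, section 10.4.2 adds staff observation and verification visits on days 7 and 28, and Table 8 requires areola to be measured at its maximum and graded. Section 10.7.4.4 does not cite 10.4.3, and Tables 8 and 10 are themselves headed as local and systemic, so areola could be classified as local from Table 8. Dizziness can be graded on the generic scale.

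Most of this stands. It rules out a stronger reading that a reader might draw: that redness is not collected and that the local and systemic rates are both wrong. The documents do not show that redness is uncollected, since Table 8 requires its measurement if areola means redness. They do not show an error in the listed systemic reactions either, for the reason in step 5. Section 14.1 is also weak support for a list of local signs, because its sentence runs fever, headache and nausea together with symptoms at the vaccination site.

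The contradiction itself remains. Dizziness is a complete and medically distinct word, and someone building a prompt list or an analysis program from 10.4.3 would have no reason to read it as areola. That Table 8 could serve as the classification instead means that the protocol holds two classifications that disagree on one term.

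**Conclusion.** The point holds as an internal inconsistency in operative safety text. Section 10.4.3 disagrees with Table 8 on one of seven local terms, and redness or areola is in neither of its lists, although the protocol grades areola and names redness as expected.

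The consequence is conditional. If 10.4.3 is used both as the prompt list and as the classification under 10.7.4.4, dizziness would count as a local reaction, and redness might not be prompted for or might be left out of the local incidence. This rests on two assumptions: that areola means injection-site redness, and that 10.4.3 is followed literally. Under-collection of redness is a risk and cannot be established without the diary card and eCRF.

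The reach is limited to the local-reaction breakdown of a secondary safety endpoint. No effect is shown on overall adverse-event incidence by MedDRA term, the listed systemic reactions, the primary endpoints or the sample size. No event count can be given, because the protocol states no expected rate for redness or dizziness. It is a minor point, worth correcting because the correction is specific and nearly free.

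**What to change.** In section 10.4.3, replace dizziness in the local list with areola (redness), so that the list agrees with Table 8 and with section 14.1. Check the diary-card and eCRF terms against the corrected list. Record any dizziness as a non-injection-site adverse event, graded by the generic scale in section 10.4.4. It would also help for section 10.7.4.4 to name 10.4.3 as the classification that it uses.

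The cost is a one-term correction, at most one added cross-reference, and a check of two term lists. No visit, procedure or sample is added.
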